4.5.2 Key Secondary Efficacy Endpoints

4.5.2.1 6-Point Ordinal Scale Measured at Day 7

For the key secondary endpoint of 6-point ordinal scale, which is recorded after randomization on Day 1, and again once daily every morning (between 8 am and 12 pm) while hospitalized, the response rate of the scale will be measured at Day 7. The ordinal scale categories are as follows:

1. Discharged (or “ready for discharge”)
2. Non-ICU hospital ward (or “ready for hospital ward”) not requiring supplemental oxygen/non-invasive ventilation
3. Non-ICU hospital ward (or “ready for hospital ward”) requiring supplemental oxygen/non-invasive ventilation
4. ICU without mechanical (invasive) ventilation (or “ready for ICU admission”)
5. Mechanical (invasive) ventilation
6. Death

Patients who are ready to be discharged (e.g., still hospitalized due to non-medical or administrative reasons) will be assigned an ordinal scale of 1.

Patients in non-ICU hospital ward that are eligible for ICU care based on clinical presentation but awaiting ICU care will be assigned an ordinal scale of 4.

Patients in ICU for administrative or non-medical reasons, who are ready for a non-ICU hospital ward, will be assigned an ordinal scale of 2 (if not requiring supplemental oxygen/ non-invasive ventilation) or 3 (requiring supplemental oxygen/ non-invasive ventilation).

The 6-point ordinal scale will be analyzed using the Cochran-Mantel-Haenszel test statistic stratified by region (i.e., North America, EMEA, ROW), NEWS2 at baseline (≤ 7 , > 7), and time from symptom onset to study treatment (≤ 48 hours, > 48 hours) for the mITTI population.

For the ordinal endpoint, missing data will be imputed as per the following rules as described in [Table 5](#) below:

Table 5 Ordinal Scale and Missing Data

Event	Imputation Rule
Patient Discontinued or Lost to follow-up (prior to Day 7)	Impute to last ordinal assessment if either 'Discharged' or 'Death' otherwise not imputed
Patient ongoing but Missing Day 7	Impute to the higher scale score of the prior and subsequent assessment

The proportion of patients with a response in each category will be summarized by treatment group and Cochran-Mantel-Haenszel test statistic result presented. Additionally, a stacked bar-chart will present the ordinal scale responses over time by treatment.

An exploratory analysis using an ordinal outcome logistic regression model will be conducted.

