4.5.16 Ordinal Scale Determination

Assessment of patient status using an ordinal scale will be recorded at baseline on Day 1, and again once daily every morning (between 8 am and 12 pm) while hospitalized. The ordinal scale categories are as follows:

1. Discharged (or “ready for discharge”)
2. Non-ICU hospital ward (or “ready for hospital ward”) not requiring supplemental oxygen/non-invasive ventilation
3. Non-ICU hospital ward (or “ready for hospital ward”) requiring supplemental oxygen/non-invasive ventilation
4. ICU without mechanical (invasive) ventilation (or “ready for ICU admission”)
5. Mechanical (invasive) ventilation
6. Death

Patients who are ready to be discharged (e.g., still hospitalized due to non-medical or administrative reasons) will be assigned an ordinal scale of 1

Patients in non-ICU hospital ward that are eligible for ICU care based on clinical presentation but awaiting ICU care will be assigned an ordinal scale of 4.

Patients in ICU for administrative or non-medical reasons, who are ready for a non-ICU hospital ward, will be assigned an ordinal scale of 2 (if not requiring supplemental oxygen/ non-invasive ventilation) or 3 (requiring supplemental oxygen/ non-invasive ventilation).

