2.4 DETERMINATION OF SAMPLE SIZE

The required sample size of the modified intent-to-treat infected (mITTI) population is 264 patients (176 patients in the baloxavir marboxil group and 88 in the placebo group). It is assumed that the reverse transcriptase polymerase chain reaction (RT-PCR)–positive rate (tested in a central laboratory) will be 75% of the randomized population; hence, approximately 366 patients will be randomized to ensure an adequate number of patients in the mITTI population and to allow for a 4% dropout rate. The total number of randomized patients may change based on the percentage of patients who are RT-PCR positive during the study.

The total mITTI sample size of 264 patients provides at least 80% power using the log-rank Chi-Square test to detect a 31-hour difference in the time to clinical improvement (TTCl) between treatment groups under the following assumptions: median TTCl in the placebo plus NAI group is 94 hours, 840 hours follow-up (35 days), using an alpha of 5%, and the minimal detectable difference is 23 hours. The TTCl in the placebo plus NAI group of 94 hours was selected after consideration of the response rates observed in a blinded review of TTCl including data from 127 patients.

The study power is calculated based on the primary endpoint incorporating a group sequential design (GSD) using a beta spending function with non-binding rule, to allow for one futility interim, without increasing the overall experiment-wise error rate.

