4.3.3 Disease Characteristics and Influenza History

- RT-PCR status (positive, negative)
- Influenza Subtype
- Time from symptom onset to study treatment
- Reason for hospitalization (Current Influenza Episode or Other (Prolonged Hospitalization))
- Seriousness criteria:
 - Required ventilation or supplemental oxygen to support respiration at baseline
 - Complication requiring hospitalization

- Complication by body system category (Cardiac, Central Nervous System [CNS], Hepatic, Renal, Respiratory, Gastrointestinal, Metabolic, Musculoskeletal, Other)
- NEWS2 at baseline
- intensive care unit (ICU) status at baseline
- Chronic Hypoxia History (Yes, No, Unknown)
- Co-infections (identified via the non-influenza respiratory bacterial and virus co-infection panel)
- Previous anti-influenza treatments
 - Vaccination history (within last 6 months, within last 12 months)
 - Antiviral treatment within 48 hours prior to screening. Type of antiviral treatment utilized will be presented e.g: Oseltamivir/oseltamivir phosphate, peramivir, zanamivir, Laninamivir, Arbidol, Favipiravir, Amantadine, Rimantadine,
- Ordinal scale at Day 1 (categories 1 – 6, see Section 4.5.2.1)

Medical history data, including surgery and procedures and ongoing baseline conditions will be summarized descriptively by treatment group using the safety population. Additionally, ongoing baseline conditions present in >5% of patients in any treatment arm will be presented. Descriptive summaries of any previous and concomitant treatment will be produced by treatment group for the safety population.

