4.5 EFFICACY ANALYSIS

Efficacy analyses will be conducted for the mITTI population. Hypothesis tests will be two-sided at the 5% significance level, unless stated otherwise.

To manage the overall type I error, the primary and key secondary endpoints will be tested sequentially. The order of testing will be as follows:

- TTCl
- Response rates of the 6-point ordinal scale at Day 7
- Time to Clinical Response

If the primary efficacy analysis hypothesis test result is not statistically significant (i.e. $p > 0.05$), the hypothesis below that result in the hierarchical chain will be considered exploratory and no claims of statistical significance will be made. The same rules apply to the next endpoint in the chain.

4.5.1 **Primary Efficacy Endpoint**

The primary efficacy objective for this study is to evaluate the efficacy of baloxavir marboxil plus a SOC NAI, compared with matching placebo plus SOC NAI based on the following endpoint:

- TTCI (defined as time from treatment start to hospital discharge or time to NEWS2 ≤ 2 and maintained for 24 hours, whichever comes first)

TTCI is calculated as per [Table 3](#).

Table 3 TTCI Calculations

TTCI based on	TTCI (hours)
NEWS2 ≤ 2 for 24 hours	date time of initial NEWS2 assessment ≤ 2 - start treatment date time
NEWS2 ≤ 2 prior to discharge*	date time of initial NEWS2 assessment ≤ 2 - start treatment date time
Hospital discharge	date time of hospital discharge - start date time of treatment

*when a patient met the NEWS2 ≤ 2 and was discharged from hospital during the 24 hour period of stability confirmation, the time of achieving TTCI was defined as the initial time at which the NEWS2 ≤ 2 and not the time of hospital discharge.

NEWS2 (National early warning score 2) is the sum of the score of each of the following assessments, as described in [Appendix 4](#): respiration rate (per minute), oxygen saturation (SpO₂%) according to scale 1 or scale 2, supplemental oxygen or room air, systolic blood pressure (mmHg), pulse rate (bpm), consciousness level, temperature (°C).

Missing data for the calculation of the NEWS2 will not be imputed for the following reasons:

1. TTCI endpoint can be met through hospital discharge.
2. The physiological components of the NEWS2 can be highly heterogeneous in the study patient population and therefore the process of imputation would not be relevant.

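### The confirmatory Day 7 ordinal test leaves out the Day 1 score on the same scale, which gives up efficiency on the endpoint that gates time to clinical response

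*SAP*

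**What the plan says.** SAP 4.5.2.1 fixes the confirmatory test, in line with protocol 6.4.2.1: "The 6-point ordinal scale will be analyzed using the Cochran-Mantel-Haenszel test statistic stratified by region". The other two strata are baseline NEWS2 cut at 7 and onset-to-treatment time cut at 48 hours. With three regions this makes 3 × 2 × 2 = 12 strata, built from the same factors as the randomisation (SAP 3.1).

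The Day 1 score exists. Protocol 4.5.16 says that the scale "will be recorded at baseline on Day 1, and again once daily every morning" during the hospital stay. SAP 4.3.3 lists "Ordinal scale at Day 1" among the characteristics to be summarised. That use is descriptive. One further model is planned: "An exploratory analysis using an ordinal outcome logistic regression model will be conducted". It has no named covariates and no confirmatory role.

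Elsewhere the SAP does adjust for a starting value: in 4.6, change in virus titre and change in RNA each take their own baseline as a covariate.

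The order of testing (SAP 4.5) is TTCI, then the Day 7 scale, then time to clinical response, and "Hypothesis tests will be two-sided at the 5% significance level, unless stated otherwise". A non-significant result on the Day 7 scale makes time to clinical response exploratory.

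**The concern.** Patients can start anywhere from category 2 to category 5. Protocol 4.3.2.1 and 4.5.13 provide for intubated patients, and SAP 4.5.3 has separate clinical-failure rules for those who start in categories 4 and 5. If the starting category predicts the Day 7 category within the 12 strata, leaving it out leaves explainable variation in the comparison and lowers power. No power is stated for this endpoint, yet it is the gate to the last endpoint in the sequence.

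NEWS2 cut at 7 takes up only part of this. ICU status is not a NEWS2 item, and the air-or-oxygen item gives the same 2 points to any form of oxygen or ventilation (protocol Appendix 3), so categories 3, 4 and 5 are separated only indirectly.

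**Working it through.** **1. The plan's own figure.** SAP 2.4 has "176 patients in the baloxavir marboxil group and 88 in the placebo group" and says that this total "provides at least 80% power using the log-rank Chi-Square test to detect a 31-hour difference", with a control median of 94 hours.

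- Analysis set: 366 × 0.75 × 0.96 = 263.5, which matches 264.
- Rate ratio: 94 / (94 − 31) = 94 / 63 = 1.492.
- Fixed design, all 264 patients counted as events: Φ(√(264 × 2/3 × 1/3) × ln 1.492 − 1.96) = Φ(7.66 × 0.400 − 1.96) = 86.5%.
- With a futility look at 65% of events, Pocock-type beta spending and the bound followed, the bound is one-sided p = 0.0772 (SAP 2.5.1 gives about 0.077) and power is 80.3%.

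The stated figure is therefore reproduced, but it concerns TTCI only. For the ordinal scale the documents give no effect size, Day 1 mix or correlation; protocol 3.3.4 says that no minimum relevant difference has been defined. Everything below rests on assumptions.

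**2. Normal approximation.** Let r be the Day 1-to-Day 7 correlation within strata. Adjusting for Day 1 divides the residual variance by 1/(1 − r²), so

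power = Φ((1.96 + z) / √(1 − r²) − 1.96), and effective N = 264 / (1 − r²),

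where z is the normal quantile of the planned test's power (0.842 for 80%). Example, r = 0.5: 2.802 / 0.866 − 1.96 = 1.275, and Φ(1.275) = 89.9%.

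| r | Power from 80% base | Power from 50% base | Effective N |
|---|---|---|---|
| 0.1 | 80.4% | 50.4% | 267 |
| 0.2 | 81.6% | 51.6% | 275 |
| 0.3 | 83.6% | 53.8% | 290 |
| 0.4 | 86.4% | 57.1% | 314 |
| 0.5 | 89.9% | 61.9% | 352 |
| 0.6 | 93.8% | 68.8% | 412 |

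**3. Simulation.** 176:88 patients in 12 strata. The Day 1 mix over categories 2/3/4/5 was either narrow (22/68/7/3%) or wide (25/45/18/12%). NEWS2 >7 was linked to the Day 1 category (log-odds 0.8 per category), and region had no effect on outcome. A control patient starting in category 3 had cumulative Day 7 probabilities of 55/75/88/93/96% for categories 1 to 5. The treatment effect was tuned to give the planned CMH (mean scores, 1 df) about 80% power. There were 3,000 trials per row (standard error about 0.7 points). A linear model on the scores stood in for the ordinal model.

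| Mix | r | Planned CMH | Day 1 as extra CMH stratum | Day 1 as covariate |
|---|---|---|---|---|
| Narrow | 0 | 78.5% | 74.8% | 78.5% |
| Narrow | 0.11 | 82.0% | 78.6% | 82.6% |
| Narrow | 0.22 | 83.8% | 82.1% | 85.3% |
| Narrow | 0.32 | 79.3% | 79.7% | 84.0% |
| Narrow | 0.41 | 80.4% | 84.6% | 87.0% |
| Wide | 0 | 81.5% | 77.3% | 81.3% |
| Wide | 0.16 | 79.2% | 76.1% | 79.9% |
| Wide | 0.32 | 77.6% | 77.2% | 82.5% |
| Wide | 0.46 | 82.7% | 86.7% | 90.5% |
| Wide | 0.56 | 80.4% | 89.3% | 93.2% |

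The covariate gains (for example 84.0 − 79.3 = 4.7 points at r = 0.32, and 93.2 − 80.4 = 12.8 at r = 0.56) agree with step 2. With no treatment effect (1,500 trials per row, standard error about 0.6 points), rejection rates were 4.4 to 5.8% for the planned CMH and 4.3 to 6.5% over all three tests.

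**4. Why a covariate and not a stratum.** Three Day 1 groups would turn 12 strata into 36, with 88 / 36 = 2.4 controls each on average; the extra-stratum column shows the cost at low r. Putting Day 1 in place of region is no safe alternative. At an odds ratio of 2.0 (1,000 trials, standard error about 1.5 points), power went from 62% to 67% with a Day 1 effect of 1.0 log-odds per category and no regional effect. It went from 67% to 66% with a Day 1 effect of 0.5 and an assumed regional effect of 0.8 per step, and from 73% to 71% with neither effect.

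**The case against.** The strongest reply is that nothing is wrong with the planned test. It stratifies by all three randomisation factors and holds its error rate. That stands. A reader might infer that a chance excess of ventilated patients in one arm would bias the result. The documents do not support this: randomisation makes such an imbalance part of the variation that the test already allows for, and stratifying by NEWS2 limits it.

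Second, NEWS2 carries more severity information than it may seem to. Oxygen or any ventilation scores 2, and any level of consciousness other than alert scores 3. The step from category 2 to 3 is thus scored directly, and a ventilated patient who is not alert starts at 5. The documents do not show how closely NEWS2 tracks the ordinal scale, so it cannot be called a weak proxy. If it tracks closely, r within strata is small and so is the gain.

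Third, the Day 1 score may not be a clean baseline. Protocol 4.5.16 places it at baseline, SAP 4.5.2.1 places it after randomisation, and neither says that it precedes the first dose. Adjusting for a score taken after dosing could remove part of the treatment effect. This stands and sets a condition on the fix.

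Fourth, an ordinal logistic model is already planned. It is exploratory and has no stated covariates, so it does not help the gate.

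**Conclusion.** The point holds as an efficiency loss on a gatekeeping endpoint. It is not a validity error. Its size depends on an unstated within-strata correlation: from an assumed 80% base, about 0 to 2 points of power for r up to 0.2, 4 to 6 for r of 0.3 to 0.4, and 10 to 14 for r of 0.5 to 0.6. The entry criteria and the NEWS2 stratum may place the trial towards the lower end. The case for change is that the covariate is already recorded and costs little.

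Two stronger readings should be resisted. A reader might quote one power loss as if it were a property of this trial; without an effect size, a Day 1 mix or a correlation in the documents, only the conditional range can be defended. A reader might also infer inflated type I error because the SAP does not say which CMH statistic it means. Taking the better of the row-mean-scores and general-association tests after seeing results gave about 8 to 10% in simulation, but nothing in the documents suggests such a choice. The unnamed statistic is a separate gap in specification and adds nothing to the size of this point.

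**What to change.** Before the sponsor is unblinded:

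- Make the confirmatory Day 7 analysis a proportional-odds model with treatment, Day 1 ordinal category (2, 3, 4–5), region, NEWS2 group and onset-time group. Report the common odds ratio with its 95% CI.
- Define the covariate as the last score before the first dose, reconcile protocol 4.5.16 with SAP 4.5.2.1 on this, and say what is done if no pre-dose score exists.
- Keep the CMH test with its planned strata, including region, as a supportive analysis, and name the 1-df row-mean-scores statistic for it.
- List the change in SAP 3.3, because protocol 6.4.2.1 also names the CMH test.

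The cost is SAP wording, provided that the recorded Day 1 scores do precede dosing. The downsides are small: the model relies on proportional odds, and the gain is negligible if Day 1 status predicts Day 7 status only weakly within strata.

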NEWS2 was developed for patients aged ≥ 16 years; however, children aged 12–16 years have very similar physiological parameter ranges as adults. In this study, NEWS2 is not being used as an early warning system to identify patients who may need escalating levels of care; rather, it is being used to standardize vital sign collection which will facilitate setting severity levels for inclusion and demonstrating response to treatment. Most pediatric early warning scores are complex and designed to detect critical illness in younger children. For the purposes of this study, a patient achieving a NEWS2 of ≤ 2 is likely to represent a meaningful degree of clinical improvement (i.e., clinically stable and potentially eligible for discharge). Importantly as well, the method of statistical analysis and the selection of a clinically meaningful difference between treatment groups are possible for an endpoint of this design.

The *first* key secondary endpoint will be the proportion of patients per category in the 6-point ordinal scale at Day 7. The categories within this scale (see Section 4.5.16) reflect the clinical status of patients during their hospital stay. The clinical status should be assessed to reflect the most accurate condition of the patient from a medical perspective, to minimize the effects of administrative or non-medical factors (e.g., the hospital bed availability may lead to patients not being cared for in the ward most suitable for their condition). This endpoint has received considerable interest for use in this patient population. There is as yet no definition of a minimum clinically relevant difference between treatment groups; however, the 6-point ordinal scale will be used in

this study to investigate the change in clinical state of patients as the key secondary endpoint.

The second of the two key secondary endpoints will be “time to clinical response”. This endpoint is defined by the time to hospital discharge or the time to vital sign parameter stabilization. Vital sign stabilization is based on achieving a set temperature, combined with achieving a set oxygen saturation, plus two out of three other parameters related to respiratory status, blood pressure or heart rate (see Section 6.5).

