6.4.2 Key Secondary Endpoints

6.4.2.1 *6-Point Ordinal Scale Measured at Day 7*

For the key secondary endpoint of 6-point ordinal scale the response rate of the scale will be measured at Day 7. The 6-point ordinal scale will be analyzed using the Cochran-Mantel-Haenszel test statistic stratified by region (i.e., North America, EMEA, ROW), NEWS2 (≤ 7 , > 7), and time from symptom onset to study treatment (≤ 48 hours, > 48 hours).

For the ordinal endpoint, missing data will be imputed by using the patient's last non-missing score for any patient with a missing response at Day 7. If the patient died

prior to Day 7, the patient will be included in the death category. The proportion of patients with a response in each category will be summarized by treatment group and Cochran-Mantel-Haenszel test statistic result presented.

A sensitivity analysis will be conducted where missing scores at Day 7 will be replaced by the patient's last non-missing score +1 (*i.e.*, *one ordinal category worse*). If the patient died prior to or on Day 7, the patient will be included in the death category.

6.4.2.2 *Time to Clinical Response*

The additional key secondary endpoint of the "time to clinical response" will be based upon hospital discharge, fever, and oxygen saturation, and two or more of the following: improved respiratory status, heart rate, or systolic blood pressure. The exact criteria for each parameter are as follows:

Temperature:^a

- $\leq 36.6^{\circ}\text{C}$ ($\leq 97.9^{\circ}\text{F}$)—axillary, or
- $\leq 37.2^{\circ}\text{C}$ ($\leq 99^{\circ}\text{F}$)—oral, or
- $\leq 37.7^{\circ}\text{C}$ ($\leq 99.9^{\circ}\text{F}$)—rectal, core, or tympanic

AND

Oxygen Saturation:^{b,c}

- $\geq 95\%$ (without supplemental oxygen)

AND two of the following three:

Respiratory Status:

- Return to pre-morbid oxygen requirement (patients with chronic oxygen use), OR
- Need for supplemental oxygen (given in any way—ventilator, non-invasive ventilation, facemask, face-tent, or nasal cannula) to no need for supplemental oxygen, OR
- Respiratory rate ≤ 24 per min (without supplemental oxygen)

Heart Rate:

- ≤ 100 beats per min

Systolic blood pressure:^d

- ≥ 90 mmHg
- OR

Hospital Discharge

- a Without the use of antipyretics within 8 hours.

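### The Day 7 ordinal test names the Cochran-Mantel-Haenszel family but not the form, scores or success direction, and its p-value gates time to clinical response

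*SAP*

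**What the plan says.** SAP 4.5.2.1 gives the confirmatory analysis in one sentence: "The 6-point ordinal scale will be analyzed using the Cochran-Mantel-Haenszel test statistic stratified by region", NEWS2 and time from symptom onset. Protocol 6.4.2.1 uses the same wording, and the sensitivity analysis in SAP 4.5.2.2 refers to the same statistic. None of the three states the form of the statistic, the category scores, the degrees of freedom or the result that counts as success.

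The endpoint is described in two ways. Protocol 6.4.2.1 says "the response rate of the scale will be measured at Day 7"; protocol 3.3.4 calls it "the proportion of patients per category in the 6-point ordinal scale at Day 7". On reporting, SAP 4.5.2.1 says: "The proportion of patients with a response in each category will be summarized by treatment group and Cochran-Mantel-Haenszel test statistic result presented". It then adds: "An exploratory analysis using an ordinal outcome logistic regression model will be conducted".

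SAP 4.5 and protocol 6.4 set a fixed sequence: time to clinical improvement (TTCI), then the Day 7 ordinal scale, then time to clinical response. A p-value above 0.05 makes the next endpoint exploratory. The general rule is: "Hypothesis tests will be two-sided at the 5% significance level, unless stated otherwise". No power or target effect is given for the ordinal endpoint; protocol 3.3.4 notes: "There is as yet no definition of a minimum clinically relevant difference".

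**The concern.** For a binary endpoint the stratified Cochran-Mantel-Haenszel (CMH) name identifies one 1-df test. For a 2-by-6 table it does not:

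- **General association** compares the whole category pattern. It has up to 5 df, ignores the ordering and has no direction.
- **Row mean scores** compares average scores. It has 1 df, tests a shift, and depends on the scores (integers 1 to 6, or modified ridits). With two arms the correlation form is the same test for the same scores.

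The text points both ways. The per-category wording, and the exploratory label on the only explicitly ordinal model, suit general association. The name of the scale and the way missing scores are handled suit a shift test. The two-sided 5% rule does not settle the form and gives no direction to a 5-df statistic.

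At stake are the power of a key secondary endpoint, the meaning of a significant result on it, and the opening of the last step in the sequence.

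**Working it through.** **Inputs from the documents.** mITTI N = 264, 176 versus 88 (SAP 2.4). Allocation is 2:1, with 3 regions × 2 NEWS2 groups × 2 onset groups = 12 strata (SAP 3.1). Alpha is 5%, two-sided (SAP 4.5).

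**The plan's own power figure.** The documents give power for TTCI only: at least 80% for a 31-hour difference from a 94-hour control median.
- N: 366 × 0.75 × 0.96 = 263.5.
- Hazard ratio, exponential: 94/63 = 1.492. Nearly all 264 patients have an event by 840 hours.
- Fixed design: √(264 × 2/3 × 1/3) × ln 1.492 = 3.065; 3.065 − 1.960 = 1.105; power 86.5%.
- With the futility look at 65% of events (Pocock-type beta spending, final critical value 1.96): 80.3%. The stated figure reproduces.

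**Assumptions, because the documents give none for Day 7.** Control percentages in categories 1 to 6: A 60/20/10/4/3/3; B 45/25/15/6/5/4; C 30/25/22/10/8/5. Stratum shares: region 25/50/25, NEWS2 65/35, onset 45/55. Effect: a common odds ratio.

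**Statistics.** G is the sum over strata of observed minus expected category counts in the active arm, and V its summed covariance.
- General association: Q = G′V⁻¹G, with df = populated categories − 1.
- Row mean scores: the same differences weighted by scores and summed, squared, and divided by the variance; 1 df.
- Modified ridit in a stratum: (patients in lower categories + (category count + 1)/2)/(stratum size + 1).

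**Results, 4,000 trials per cell, % significant.** Monte Carlo standard error is √(0.05 × 0.95/4000) = 0.3 points at 5% and √(0.5 × 0.5/4000) = 0.8 points at 50%.

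| Control | Odds ratio | General association | Row mean, integer | Row mean, ridit | Better of first two | Best of three |
|---|---|---|---|---|---|---|
| A | 1.0 | 4.5 | 4.6 | 4.7 | 8.0 | 9.6 |
| B | 1.0 | 4.6 | 4.7 | 5.0 | 8.0 | 9.3 |
| C | 1.0 | 4.4 | 4.5 | 4.6 | 7.9 | 8.8 |
| A | 1.5 | 20.9 | 29.9 | 34.4 | – | – |
| B | 1.5 | 22.8 | 35.1 | 38.2 | – | – |
| C | 1.5 | 23.9 | 39.3 | 40.4 | – | – |
| A | 2.0 | 50.4 | 63.3 | 71.3 | – | – |
| B | 2.0 | 59.3 | 74.4 | 79.7 | – | – |
| C | 2.0 | 61.8 | 79.2 | 81.8 | – | – |

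General association and integer row mean scores fall on opposite sides of 5% in about 7% of null trials and in 20-28% of trials at odds ratios 1.5 to 2.0.

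Further runs, with other assumed distributions placing 45-70% of controls in category 1, widen the ranges. At odds ratio 2.0, general association has about 42-58% power against about 63-80% with ridits. At 1.5 it is about 18-23% against 29-39%. The better of two forms has null error of about 6-9%, and the best of three about 9-10%.

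**Analytic cross-check.** A 1-df test with 80% power has noncentrality (1.960 + 0.842)² = 7.85. If the effect lies wholly along the scores, a 5-df test with that noncentrality has 55.5% power. At 90% (10.51) the 5-df figure is 70.3%.

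**Direction.** Take control B and an assumed active arm of 55/10/13/8/8/6. More active patients are discharged, and more are also in categories 4 to 6 (22% versus 15%). Mean scores are:
- control: 0.45 + 0.50 + 0.45 + 0.24 + 0.25 + 0.24 = 2.13;
- active: 0.55 + 0.20 + 0.39 + 0.32 + 0.40 + 0.36 = 2.22, slightly worse.

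General association rejects in 72.9% of trials and row mean scores in 5.6% (6.2% with ridits).

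**The gate.** If neither TTCI nor the ordinal scale has an effect, a false ordinal claim stays at or below 5%, because TTCI must pass first. If TTCI has a true effect, its power is 80% and the two tests are independent, the unconditional error is 0.80 × 8.0% = 6.4% (two forms) or 0.80 × 9.6% = 7.7% (three). A fixed 5% test gives 0.80 × 5% = 4.0%. Positive correlation raises these.

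**The case against.** Much of the text treats the categories as ordered. SAP 4.5.2.1 fills a missing Day 7 score with the worse of the neighbouring assessments, and the protocol's sensitivity analysis moves a missing patient one category worse. The per-category sentence describes the summary table, not the test. Direction would also be visible in that table, the stacked bar chart and the ordinal model. This stands: a reader might infer that the plan commits to general association, and the documents do not support that. It does not close the gap, because none of this text names the test and none of the displays is the gate.

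A reader might also infer that the form will be chosen with results in hand. The documents do not show this. Protocol 6.7.1 and SAP 2.5.1 keep the sponsor blinded until the end of the study, and table shells or programming specifications, which are not part of these documents, may already fix the form.

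Finally, the response-rate label might suggest a responder dichotomy. No cut-point is defined and protocol 3.3.4 describes all categories, so that reading has little support.

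**Conclusion.** The point holds as an unspecified confirmatory test. The power loss from the literal 5-df reading is material: at an odds ratio of 2.0, about 42-58% against about 63-80%. At 1.5 both forms are weak. The figures depend on assumed Day 7 distributions, stratum shares and a proportional-odds effect. The ordering of the two forms held in every set tried under that effect. Five df also requires all six categories to be populated.

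The error figures of about 6-9% and 9-10% are conditional. They need TTCI to be significant, no true ordinal effect, and the smallest p-value to be taken. A reader might turn them into a claim that the trial's error rate is 10%; the fixed sequence does not support that. Each form holds about 5% when fixed in advance. The choice between integer and modified ridit scores is a preference; leaving it open is the defect.

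**What to change.** Before unblinding, state in SAP 4.5.2.1, and by reference in 4.5.2.2, that:

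- the confirmatory test is the stratified CMH row mean scores statistic (1 df) with one named score set, integer or modified ridit;
- the step passes only if p ≤ 0.05 and the shift favours baloxavir, judged by the sign of the same stratified score difference (lower categories are better);
- any general association result is descriptive and does not open the test of time to clinical response;
- the odds ratio and 95% CI from the ordinal logistic model already planned are reported as the effect estimate.

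Protocol 6.4.2.1 should be read consistently with this. The cost is a few sentences of SAP text and no new data. The downside is that a difference in category pattern with no overall shift would not count as success.
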